2. STATISTICAL ANALYSIS

a. Analysis of data/study outcomes

The double blind will be broken and the randomization status of each participant will be revealed only after the completion of this study in all 20 individuals. An interim **blinded** analysis may be performed no more than one time (for example, at the request of the PI's Board of Scientific Counsellors) to inform ongoing scientific efforts and productivity of the Branch; however, this interim analysis will not serve as the basis for decisions to change study procedures or to terminate the study. (**Specific Aim 1**) To assess the efficacy of AV-101 compared with placebo in improving overall depressive symptomatology over a two-week course of treatment in patients with treatment-resistant MDD currently experiencing a major depressive episode.

The primary aim will be accomplished by assessing the efficacy of two weeks of oral AV-101 (1,080 or 1,440 mg/day) compared with placebo in improving overall depressive symptomatology. The primary assessment of efficacy is a comparison of HDRS scores between treatment groups.

The difference between AV-101 and placebo will be examined using a linear mixed model with restricted maximum likelihood estimation where drug and time are within subjects factors. Drug and time main effects and their interaction will be included in the model as within subjects factors. Baseline scores for each phase will be used as a time-dependent covariate. A random intercept and subject effect will be included if they contribute significantly to the model. Schwarz's Bayesian criteria will be used to examine the most appropriate covariance structure prior to formal analyses, where a compound symmetry structure will be used in another is not preferred. Bonferroni corrected post hoc tests will be used to follow up on a significant drug by time interaction. Cohen's d will be calculated to describe the effect size.

Additional follow-up analyses may examine the potential for carryover effects within the crossover study. First, an additional phase variable may be added to the original statistical model. Second, results in the first phase of the study may be examined separately to understand whether any drug effect remains in a parallel-like design.

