Secondary analyses will be conducted in the same manner for BPRS, CADSS, C-SSRS, HAM-A, MADRS, PANAS, SHAPS, SSI, TEPS, and YMRS. A similar statistical model will be used to examine secondary measures. Bonferroni-like corrections will be used to determine the significance of secondary analyses.

Criteria for significance

Significance will be evaluated at p<.05, two-tailed.

Analyses will be based on the intent-to-treat (ITT) principle where all randomized subjects who receive baseline and at least one post-baseline assessment will be included. A subject will be considered a responder if the HDRS total score has decreased by 50% or more from baseline to endpoint. Response rates will be analyzed using McNemar's test for repeated measures categorical outcomes.

Safety and tolerability assessments will be based on the safety analysis set which will include all randomized subjects who are given study treatment.

The incidence rate of adverse events will be tabulated by preferred term and system organ class; serious adverse events, adverse events leading to death, and adverse events leading to withdrawal of subjects will be tabulated for each treatment group.

Analyses of surrogate neurobiological markers

Multiple logistic regression models (for categorical outcome, response vs. non-response) will evaluate candidate biological markers for independent association with outcomes. For these models, we will compute robust standard errors or associated 95% confidence intervals.

PI name: [name]
Protocol number: 15-M-0151

Date: 05-15-18
Version:Am C

b. Power analysis

Previous studies by our group (see **Background**) demonstrated improvement in depression at 72 hours with an effect size of d=0.67. Assuming α =.05, two-tailed, 20 patients with MDD would provide 81% power to detect an effect of the same size as previously reported with a double-blind crossover study. We are primarily interested in detecting drugs with a large effect size that occurs within a short period of time (\leq 72 hs) as there are already many antidepressants with small effect sizes after 2 weeks of treatment. This is the reason for not studying a much larger number of patients; in addition, the current study design uses a crossover design.

c. Accrual number

If we assume that 20% of subjects will either not complete the drug free period or will drop out during the crossover double-blind portion of the study, then 25 MDD patients need to be recruited.

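### The logistic marker models in about 20 patients use robust standard errors with no stated small-sample correction; if uncorrected, their intervals tend to be too narrow, and Firth's penalised likelihood is a cheap improvement

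*Combined protocol and SAP*

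**What the plan says.** The paragraph on surrogate neurobiological markers in section 2.a sets out the model: "Multiple logistic regression models (for categorical outcome, response vs. non-response) will evaluate candidate biological markers for independent association with outcomes". The sentence on precision follows: "For these models, we will compute robust standard errors or associated 95% confidence intervals". The general criterion in the same section is "Significance will be evaluated at p<.05, two-tailed".

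The number of patients comes from two places. Section 2.a ties unblinding to completion in 20 individuals, and section 2.b says "20 patients with MDD would provide 81% power to detect an effect of the same size".

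For the marker models the plan does not state:
- the version of the robust estimator
- any small-sample correction
- the reference distribution (normal or t)
- the number of markers per model
- the expected response rate
- whether each patient contributes one record or two

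**The concern.** Robust (sandwich) standard errors are justified by large-sample theory. They are built from squared residuals, and in a small sample the fit pulls those residuals towards zero. The uncorrected standard error then tends to be too small and the normal-based interval too short. The effect grows as the rarer outcome becomes scarcer and as more markers share the model. An analysis aimed at independent associations invites several markers.

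At stake is the credibility of any claim that a marker is associated with response. Section 1.b makes the relation between markers and antidepressant response an aim, and section 1.c lists surrogate biomarkers among the secondary measures. An interval labelled 95% that covers less often yields more spurious markers than the reader is told to expect.

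**Working it through.** **The plan's own figure.** The documents state no error rate for the marker models, so the only figures to reproduce are the sample size and power.
- Inputs from section 2.b: d = 0.67, N = 20, two-sided α = 0.05.
- Paired t-test: non-centrality = 0.67 × √20 = 2.996 on 19 df, giving power 81.1%. This matches the stated 81%.
- The normal approximation gives 85.0%, so the choice between t and normal already matters at this size.
- Accrual: 20 / (1 − 0.20) = 25, as in section 2.c.

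**Assumptions, not document figures.** Response rates of 20%, 30% and 50%, that is 20 × 0.2 = 4, 20 × 0.3 = 6 and 20 × 0.5 = 10 responders. One to four independent normal markers per model, none related to response. One record per patient.

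**Formulas.** With fitted probability p̂ᵢ and covariate vector xᵢ, the uncorrected sandwich is V = A⁻¹BA⁻¹, where A = Σ p̂ᵢ(1−p̂ᵢ)xᵢxᵢ′ and B = Σ (yᵢ−p̂ᵢ)²xᵢxᵢ′. A marker is called significant if |b/SE| > 1.96. The simple correction multiplies V by n/(n−p), with p the number of coefficients. For one marker plus intercept the SE is multiplied by √(20/18) = 1.054; for three markers by √(20/16) = 1.118.

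**Simulation under the null.** There were 4,000 datasets per cell. Those with fewer than 2 responders or 2 non-responders were dropped, and separated fits were excluded. Monte Carlo error is about 0.3 to 0.6 points. Per-marker false-positive rate, uncorrected sandwich with normal reference, n = 20:

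| Response rate | 1 marker | 2 markers | 3 markers | 4 markers |
|---|---|---|---|---|
| 20% | 7.2% | 8.9% | 10.0% | 11.2% |
| 30% | 6.6% | 6.7% | 8.1% | 9.3% |
| 50% | 5.0% | 6.3% | 7.2% | 8.6% |

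Coverage of the nominal 95% interval is 100% minus these values, about 89% to 95%.

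**Checks on cause and stability.**
- With one marker at 30% response, the median robust SE is 0.53 against a trimmed SD of the estimates of 0.66. The ratio is 0.53/0.66 = 0.80. It shows the direction only; the rejection rate of 6.6% in that cell is the direct measure.
- With two markers at 30% response, the error is 5.0% at n = 50 and 4.9% at n = 100. Sample size is the cause.
- At n = 25 the range is 5.2% to 9.7%.
- An independent repeat gave 4.7–6.9% with one marker and 6.5–10.3% with three. A further set that also used heavy-tailed and skewed markers gave 5.2–8.5% and 6.3–10.0%.

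**Alternatives at n = 20.**

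| Method | Per-marker false-positive rate |
|---|---|
| Sandwich × n/(n−p), normal reference | 3.9–6.3% (3.3–7.0% in a repeat) |
| Sandwich × n/(n−p), t reference | 2.4–4.4% |
| HC3 sandwich, normal reference | 0.2–2.4% |
| Model-based Wald | 0.5–2.4% |
| Ordinary likelihood-ratio test | 6–9.5% |
| Firth penalised likelihood-ratio test | 3.5–4.8% (3.8–5.3% in a repeat) |

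In the set with heavy-tailed and skewed markers, Firth gave 2.4–4.8%, so it can be mildly conservative.

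**Separation.** With three markers at 20% response, about 5% of datasets separate, and ordinary maximum likelihood then has no finite estimate. With four markers, 12% separate or fail to converge.

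**Two records per patient, if ever used.** With 20 clusters and one to three markers, the uncorrected cluster-robust test gives 6.9–10.5%. A G/(G−1) correction (20/19) with t on 19 df gives 4.4–7.4%.

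**The case against.** The strongest reply is that the plan never says the estimator is uncorrected. A reader might infer that the intervals are too narrow as a matter of fact, but the text does not support that. An ordinary n/(n−p) correction largely removes the inflation, and HC3 errs the other way. This stands, and the point is therefore conditional.

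A reader might also infer that false marker findings run at double the nominal rate. That too goes beyond the documents. With one record per patient, 10% or more appears only with about 4 responders and three or more markers. With one marker and 50% response there is no inflation. Since no response rate or marker count is given, the extreme corner cannot be presented as the expected case.

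The two-record setting is also not in the plan. Section 1.b speaks of response to AV-101, which reads more naturally as one record per patient.

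The marker models also do not enter the primary mixed-model analysis of HDRS or the safety tabulations. And naming n/(n−p) with a t reference would control the error in the one-record case without a change of method.

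What remains is that the false-positive rate can lie anywhere from under 3% to over 10% depending on an unstated default. No variance correction addresses separation, because the estimate itself fails.

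**Conclusion.** The point holds in conditional form. If the usual uncorrected sandwich with a normal reference is applied to about 20 patients, the per-marker false-positive rate is about 5–7% with one marker and 6.5–10% with three. This assumes 20% to 50% response, independent markers and one record per patient. The excess over 5% thus runs from nothing to about 5 percentage points. With a standard small-sample correction most of it disappears, and the plan does not say which applies. This is a cheap improvement to a secondary analysis, not a defect that threatens the trial's main conclusion.

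**What to change.** Replace the sentence on robust standard errors in section 2.a with: *Logistic marker models will use Firth's penalised likelihood, with profile penalised-likelihood 95% confidence intervals and tests.* Add: *If both phases per patient are entered, a small-sample-corrected cluster variance with a t reference will be used.* The simple G/(G−1) version still leaves up to 7.4% with three markers, so the correction should be named.

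Merely deleting the word robust would not do. The model-based Wald test is very conservative here, and the ordinary likelihood-ratio test is itself inflated.

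The cost is SAP wording and a standard software option, with no effect on patients, sample size or the primary analysis. The downside is somewhat wider intervals, so fewer markers will reach significance.
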